9. BIOMARKER, CORRELATIVE, AND SPECIAL STUDIES

9.1 Specimen Requirements for Correlative Studies

In this study, we propose several correlative studies, as detailed below. These assays are specifically chosen to provide information on immunologic markers that may be predictive of treatment responses as well as specific information related to the mechanism of action of the study drugs. Six integrated biomarker studies have been included; all other correlative studies will be exploratory in nature. They are intended to be hypothesis-generating and will help us advance our understanding of the systemic immunologic environment.

Submission of archived tumor tissue is mandatory *if archived tissue is available from a prior biopsy or surgery; do not* perform a biopsy solely to provide tissue for this correlative study. All tumor biopsy tissue will be submitted in either slides or formalin-fixed paraffin-embedded (FFPE) tissue blocks and will be used to produce specimens for an exploratory biomarker study of tissue expression of PD-L1.

Serial collection of peripheral blood is also mandatory for patients participating in this study. Peripheral blood will be collected at pre-study, day 1 of each cycle, cycle 1 day 8 and cycle 3 day 8. Peripheral blood will be used to assay the 1) pharmacokinetics of anetumab raptansine; 2) presence of anti-anetumab raptansine antibodies; 3) megakaryocyte potentiating factor; 4) mononuclear Phagocyte System (MPS) - Fc-gamma-receptors (Fc γ R); 5) chemokine mediators of mononuclear phagocyte system; 6) Bim in tumor reactive T cells T_{TR} and 7) soluble PD-L1.

Any surplus of blood, plasma, serum, DNA, cells and tissue will be banked at Mayo Clinic for additional studies for the patients who provide additional consent for specimen banking. If consent for specimen banking was not provided by the patient, the remaining blocks or slides will be returned to the original institution and the remaining blood, plasma, serum, DNA and cells will be discarded if the patient did not provide consent for

banking of specimens.

Summary Table for Specimen Collection

All correlative specimens in the table below are required unless noted otherwise.

Study and Time Point(s)	Specimen and Quantity	Send Specimens to:
Baseline		
Mesothelin expression Ph 1: Pre-study (only if available); Ph 2: Pre-registration	FFPE block OR 5-10 X 4-5 μ unstained, positively charged slides from archival tissue OR Fresh tissue (Ph 2 only)	Hematogenix Laboratory Services (HLS)
Tissue expression of PD-L1 ¹ (only if available)	FFPE block OR 3-5 X 4-5 μ unstained, positively charged slides from archival tissue	Mayo Clinic
MPF	4 mL whole blood in red tube top	[name], NCI
Bim in T _{TR}	10 mL whole blood in EDTA (purple top) tube	Mayo Clinic
sPD-L1		
Cycle 1 Day 1		
PKs ³ : 
• Pre-treatment;• end of anetumab ravtansine infusion²;• 7 hrs post-anetumab ravtansine infusion².	Whole blood in 1 X 3 mL lavender top EDTA tube per time point AND Whole blood in 1 X 2.7 mL lavender top EDTA monovette per time point	Covance
ADA ³	Whole blood in 1 X 4 mL gold top SST	Covance
MPS-chemokine mediators	Whole blood in 1 X 5 mL gold top SST processed to serum	[name], UNC
MPS-FcYRs	20 mL whole blood in K2 EDTA (purple top) tubes processed to PBMCs	[name], UNC
Cycle 1 Day 8		
PKs ³ : 
• Any time	Whole blood in 1 X 3 mL lavender top EDTA tube per time point AND Whole blood in 1 X 2.7 mL lavender top EDTA monovette per	Covance

Study and Time Point(s)	Specimen and Quantity	Send Specimens to:
	time point	
MPS-chemokine mediators	Whole blood in 1 X 5 mL gold top SST processed to serum	[name], UNC
MPS- FcγRs	20 mL whole blood in K2 EDTA (purple top) tubes processed to PBMCs	[name], UNC
Cycle 2 Day 1		
MPF	4 mL whole blood in red top tube	[name], NCI
Bim in T _{TR}	10 mL whole blood in EDTA (purple top) tube	Mayo Clinic
sPD-L1		
Cycle 3 Day 1		
MPS-chemokine mediators	Whole blood in 1 X 5 mL gold top SST processed to serum	[name], UNC
MPS-FcγRs	20 mL whole blood in K2 EDTA (purple top) tubes processed to PBMCs	[name], UNC
ADA ³	Whole blood in 1 X 4 mL gold top SST	Covance
Cycle 3 Day 8		
MPS-chemokine mediators	Whole blood in 1 X 5 mL gold top SST processed to serum	[name], UNC
MPS-FcγRs	20 mL whole blood in K2 EDTA (purple top) tubes processed to PBMCs	[name], UNC
Cycle 4 Day 1		
MPF	4 mL blood in red top tube	[name], NCI
Bim in T _{TR}	10 mL whole blood in EDTA (purple top) tube	Mayo Clinic
sPD-L1		
Cycle 6 Day 1		
ADA ³	Whole blood in 1 X 4 mL gold top SST	Covance
Cycle 9 Day 1 then every 3 months through 1 year from registration then every 6 months through 2 years from registration		
ADA ³	Whole blood in 1 X 4 mL gold top SST	Covance

¹Testing for mesothelin expression should take priority over testing for PD-L1 expression.

² Samples should be drawn within +/- 15 minutes of the stated time point.

³ These may be discontinued for patients who discontinue treatment with anetumab ravidansine.

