5. TREATMENT PLAN

5.1 Agent Administration

Treatment will be administered on an outpatient basis. Reported adverse events and potential risks are described in Section 7. Appropriate dose modifications are described in Section 6. No investigational or commercial agents or therapies other than those described below may be administered with the intent to treat the patient's malignancy.

Phase 2, Group 1: Pembrolizumab Alone

MK-3475 (Pembrolizumab) will be administered as a dose of 200 mg using a 30-minute IV infusion. Infusion timing should be as close to 30 minutes as possible; however, a window of minus 5 minutes and plus 10 minutes is permitted (i.e., infusion time is 30 minutes: minus 5 minutes to plus 10 minutes). Treatment with pembrolizumab may continue for up to 24 months total. Refer to Section 5.1.2.

Phase 1 and Phase 2, Group 2: Anetumab ravidansine and Pembrolizumab

Pembrolizumab will be administered as described for Group 1; anetumab ravidansine will be administered at 6.5 mg/kg as determined by the phase 1 safety lead-in portion of the study using

a 60-minute IV infusion. Infusion timing should be as close to 60 minutes as possible; however, a window of minus 5 minutes and plus 10 minutes is permitted (i.e., infusion time is 60 minutes: minus 5 minutes to plus 10 minutes). The study drugs are administered in the following order when given together: anetumab raptansine first followed by pembrolizumab. Treatment with anetumab raptansine may continue for up to 12 months total. Treatment with pembrolizumab may continue for up to 24 months total. For patients receiving both drugs, the intravenous catheter must be flushed with either D5W or 0.9% sodium chloride between the two infusions. Pre-medication is not needed unless a patient develops an infusion reaction. Refer to sections 5.1.1 and 5.1.2.

Phase 1 Dose Safety Run-In Schedule

Dose De-Escalation Schedule for Phase 1 Study ^{1,2}		
Dose Level	Dose	
	Anetumab ravidansine (mg/kg)	Pembrolizumab (mg)
1*	6.5	200
-1	5.5	200
-2	4.5	200

1. Both agents will be given every 21 days. Anetumab ravidansine will be administered prior to pembrolizumab.
 2. In obese patients, anetumab ravidansine dose should be calculated considering a maximum weight of 100 kg

* Starting dose level

Randomized Phase 2 Dose Schedule

Dose Schedule for Randomized Phase 2 Study					
Agent	Premedication; Precautions	Dose	Route	Schedule	Cycle Length

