5.1.1 Anetumab Ravtansine

Administer anetumab ravtansine as an IV infusion over 1 hour. Please refer to section 8.1.1 for compatible infusion set materials including the in-line filter.

No specific prophylactic medications are recommended for anetumab ravtansine. Full supportive care is recommended as per community standards of medical care as determined by the treating physician; however, patients should not take any medications or substances that are strong inhibitors or inducers of CYP3A4 including herbal preparation containing CYP3A4 inducers (e.g. St. John's Wort), grapefruit and grapefruit juice (CYP3A4 inhibitor) within 2 weeks before the start of study treatment or while on treatment because DM4 is a substrate of CYP3A4. Because the lists of these agents are constantly changing, it is important to regularly consult a frequently-updated medical reference for a list of drugs to avoid or minimize use of.

If a patient experiences a CTCAE Grade ≥ 2 anetumab ravtansine infusion reaction or other CTCAE Grade ≥ 2 hypersensitivity event deemed at least possibly related to anetumab ravtansine, the infusion of anetumab ravtansine will be interrupted. If treatment interruption is caused by a CTCAE Grade ≥ 2 anetumab ravtansine infusion reaction or other CTCAE Grade ≥ 2 hypersensitivity event deemed at least possibly related to anetumab ravtansine, treatment may be re-started at the time determined at the investigator's discretion. Re-treatment should be at the infusion rate reduced by 50%, along with anti-allergic prophylaxis (e.g. anti-histamines, acetaminophen, and/or corticosteroids) chosen at the investigator's discretion or according to the institutional guidelines.

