- g: For Phase 2, submission of a tissue sample at pre-registration is required to perform the mesothelin expression assay to establish eligibility. Archived tumor tissue may be submitted; if archived tumor tissue is not available to establish eligibility, a fresh tumor tissue sample must be obtained by biopsy. If a biopsy is required, it may be performed ≤ 28 days prior to start of therapy. For Phase 1 subjects, submission of archived tumor tissue, if available, is required for mesothelin expression testing. Please refer to Section 9.
- h: For subjects in both Phases 1 and 2, submission of a stored tissue sample is mandatory, *if available*, for the tissue expression of PD-L1: do **not** perform a biopsy solely to provide tissue for this correlative. Tumor tissue may be submitted as blocks or slides; please refer to section 9.

i: Blood samples for correlates are collected as follows (see also Section 9):

- 1) Phase 1 and Phase 2 Group 2 patients only: Pharmacokinetics of anetumab raptansine (including anetumab raptansine ADC, anetumab raptansine total antibody, and DM4/DM4-Me) on C1D1: pre-treatment, end of anetumab raptansine infusion (+/- 15 minutes), and 7 hours after the end of anetumab raptansine infusion (+/- 15 minutes); C1D8: any time. Note: These may be discontinued for patients who discontinue anetumab raptansine.
- 2) Phase 1 and Phase 2 Group 2 patients only: Anti-anetumab raptansine antibodies (including anetumab raptansine ADA and neutralizing antibodies) pre-dose on Day 1 of Cycles 1, 3, 6 and 9 and pre-dose every 3 months after cycle 9 in the first year and every 6 months in the second year of treatment. Note: These may be discontinued for patients who discontinue anetumab raptansine.
- 3) Megakaryocyte Potentiating Factor: pre-study, C2D1, and C4D1.
- 4) Mononuclear Phagocyte System-Fc γ R: C1D1, C1D8, C3D1 and C3D8.
- 5) Chemokine Mediators of Mononuclear Phagocyte System: C1D1, C1D8, C3D1 and C3D8.
- 6) Bim in Tumor Reactive T cells and soluble PD-L1: pre-study, C2D1, and C4D1.

j: For sites and patients that agree to participate, PRO-CTCAE is completed by ePRO application on patients' personal devices or on a tablet kept at the study site weekly during the first 3 cycles and at off-study. Questionnaires should be administered prior to treatment on days study treatment is administered. See Appendices C and D.

k: Off-study evaluation to be performed at 30 ± 3 days after the last dose of study drug.

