13.5.5 The Pharmacokinetics of Anetumab ravidansine

The analysis of the pharmacokinetics of anetumab ravidansine (including anti-drug conjugate (ADC) anetumab ravidansine, total antibody, DM4 (BAY 1006640) and DM4-Me (BAY 1006641)) will be largely descriptive. Changes over time will be plotted and assessed for each patient.

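### The ±15-minute window lets the end-of-infusion anetumab PK sample be drawn during the infusion, where it can read up to about 25% low for intact conjugate and total antibody

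*Combined protocol and SAP*

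**What the plan says.** Section 9.1 (Summary Table for Specimen Collection) lists three anetumab PK draws on Cycle 1 Day 1: before treatment, at "end of anetumab ravtansine infusion²", and 7 hours after the infusion. One further draw is taken at any time on Day 8. Footnote 2 is attached to the second and third draws: "Samples should be drawn within +/- 15 minutes of the stated time point". Section 10, calendar footnote i(1), gives the same window: "end of anetumab raptansine infusion (+/- 15 minutes".

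Section 5.1 specifies "a 60-minute IV infusion. Infusion timing should be as close to 60 minutes as possible" and allows 55 to 70 minutes: "infusion time is 60 minutes: minus 5 minutes to plus 10 minutes".

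The PK analysis in section 13.5.5 is descriptive: "Changes over time will be plotted and assessed for each patient". Section 13.5.7 regresses the Fcγ-receptor and chemokine measures on anetumab levels without saying which levels. Neither section says whether nominal or actual draw times are used.

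**The concern.** A symmetric window suits a sample taken when levels change slowly, as at 7 hours. The end of an infusion is a turning point: the level climbs steeply until the pump stops and, for an antibody, falls slowly afterwards. The early half of the window lies inside the infusion, so a sample that follows the protocol may measure a partly delivered dose.

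Early and late draws do not cancel, because only the early side moves the value materially. Pharmacokinetics is secondary objective 1.2.3, and factors affecting it are objective 1.2.4. Only three post-dose samples are taken per patient, and this is the only one placed at the end of drug input. Timing error here could be read as part of the between-patient variability that the study wants to explain.

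**Working it through.** The documents state no figure for timing error, so there is none to reproduce.

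**Inputs from the documents**
- Window: ±15 minutes (section 9.1 footnote 2; calendar footnote i(1)).
- Infusion length T: 60 minutes, 55 to 70 allowed (section 5.1).
- The sample is taken in Cycle 1, so the pre-dose level is taken as zero.

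**Assumptions**
- Constant infusion rate, one compartment, first-order elimination.
- Half-life: none is given for anetumab, so it is varied. Section 2.3.1 describes antibodies of this kind as typically having low clearance, which favours the slow end of the range.

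**Formulas**, with k = ln 2 / half-life
- Draw 15 minutes early, no elimination: shortfall = 15/T.
- Draw 15 minutes early, with elimination: shortfall = 1 − (1 − e^(−k(T−15))) / (1 − e^(−kT)).
- Draw 15 minutes late: shortfall = 1 − e^(−15k).

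**Shortfall against the true end-of-infusion level**

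| Assumed half-life | Early, T = 55 | Early, T = 60 | Early, T = 70 | Late |
|---|---|---|---|---|
| No elimination | 27.3% | 25.0% | 21.4% | 0% |
| 72 h | 27.2% | 24.9% | 21.3% | 0.2% |
| 24 h | 27.0% | 24.7% | 21.1% | 0.7% |
| 6 h | 26.2% | 23.9% | 20.3% | 2.8% |
| 2 h | 24.2% | 21.9% | 18.2% | 8.3% |
| 1 h | 21.3% | 18.9% | 15.2% | 15.9% |

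At 60 minutes the early-edge shortfall is 24–25% for any half-life of about 6 hours or more. The strong asymmetry between early and late draws depends on slow elimination; at a 1-hour half-life it has nearly gone.

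**Inside the window (T = 60, no elimination).** A draw 5 minutes early reads 5/60 = 8.3% low; 10 minutes early, 10/60 = 16.7% low.

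**Illustrative average.** The documents say nothing about how draws would be spread. If they were even over ±15 minutes at T = 60, half would be early, with a mean shortfall of 7.5/60 = 12.5%. The overall mean shortfall is then 12.5%/2 ≈ 6%. The mean square is ½ × 0.25²/3 = 0.0104, the variance 0.0104 − 0.0625² = 0.0065, and the SD about 8%.

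**After the change.** With a window of 0 to +15 minutes, only the late column applies: at most 0.7% for a half-life of 24 hours or more.

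**Which analytes.** The model describes infused material, that is, the intact conjugate and total antibody. DM4 and DM4-Me are released from the conjugate and need not be highest at the end of infusion, so none of these figures applies to them.

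**The case against.** The strongest reply is that little in the planned analysis rests on this one value.

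- **No peak analysis is planned.** A reader might infer that a peak-level summary is biased. Section 13.5.5 names no Cmax and no summary by nominal time point; it plots each patient over time. The inference is not supported.
- **No outside comparison is planned.** A reader might also infer that exposure in the combination would look lower than it is. PK samples come only from Phase 1 and Group 2, all on the combination, and no comparison with anetumab alone is specified. That inference is not supported either.
- **The regressions may not use this value.** Section 13.5.7 does not say which levels enter. The hypotheses in sections 9.3.4 and 9.3.5 concern clearance, for which the 7-hour and Day 8 samples are informative. An extra 8% is also small beside wide between-patient spread: with an assumed CV of 25–40%, √(25² + 8²) ≈ 26% and √(40² + 8²) ≈ 41%. This stands, and it limits the consequence.
- **The 7-hour sample is a partial check.** For half-lives of 24 to 120 hours it should read 2^(−7/24) = 82% to 2^(−7/120) = 96% of the end-of-infusion level. A draw at the early edge (75%) would then be followed by a higher 7-hour value, visible in the plots. A draw 5 or 10 minutes early (91.7% or 83.3%) would not stand out if the half-life were 24 hours.
- **The laboratory manual was not available.** Section 9.3.1 refers sites to it, and it may require a post-infusion draw or exact times. Exact times would allow correction, but the protocol's own window would still permit the early draw.

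What survives is narrow: the written window itself permits the wrong sample, and nothing in the supplied text prevents that.

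**Conclusion.** The point holds as a cheap improvement to a secondary measurement. At the early edge of the window, the value can be up to about 25% below the true end-of-infusion level (21–27% for infusions of 70 down to 55 minutes). This is for intact conjugate and total antibody, with a constant rate and little elimination during the infusion. It is a worst case, not an average; the 6% mean above rests on an even spread of draw times that the documents do not describe.

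The error may add one-sided noise to the end-of-infusion value in the descriptive PK, and to the marker regressions if that value is among the levels used. The primary response comparison, its sample size and its significance level are untouched.

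**What to change.** In section 9.1 footnote 2 and calendar footnote i(1), set the window for the end-of-infusion sample to 0 to +15 minutes after the infusion is complete. Keep ±15 minutes for the 7-hour sample. Ask sites to record the actual infusion stop and draw times.

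For samples already taken, plot and analyse by actual draw and infusion-stop times where these were recorded, and flag draws made before the stop so that they are not labelled end-of-infusion. They need not be discarded when actual times can be used. The documents do not show that these times were captured, so this step depends on what the site records hold.

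The cost is two footnote edits, a check of recorded times and a slightly narrower draw window for sites. No extra sample, visit or patient is needed.

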9.2 Integral Laboratory Studies

9.2.1 Mesothelin Expression

Anetumab ravidansine is an IgG1 antibody-drug conjugate that recognizes mesothelin and is bound to a potent microtubule inhibitor, DM4. Patients in Phase 2 of the study will be selected for participation in this clinical trial based on mesothelin expression by immunohistochemistry (clone SP74).

Please refer to Hematogenix lab manual for additional instructions.

9.2.1.1 Collection of Specimen(s)

Archival formalin fixed tumor tissue can be submitted in blocks or in freshly cut sections, depending on availability. Fresh core biopsies may also be submitted if archival tissue is not available or sufficient for testing.

If tissue is provided in sections, unstained slides should be provided: minimum of 5 slides of 4-5 microns thickness. Sections must be mounted on positively charged glass slides of the correct type – Super frost® Plus Micro Slides (positively charged microscope slides).

Fine needle aspiration (FNA) material is not acceptable.

9.2.1.2 Handling of Specimens(s)

For the archival specimens, storage temperatures ranges between 15°C and 25°C are preferred. Mesothelin stability on cut slides is not expected to exceed 7 months.

For fresh core biopsies, if the size of the material is larger than 3 mm, please cut the tumor into 2 pieces to allow for formalin penetration and fixation. Transfer the tumor biopsy to the container of 10% neutral-buffered formalin (NBF) as soon as possible (within 15 minutes) of tumor removal. The formalin solution should be at least 10 times the volume of the tumor specimen. Allow the tumor biopsy to stay in formalin for 24 hours +/- 1 hour at 4°C. Transfer the tumor biopsy to the vial containing 70% histology alcohol. Dispose of the 10% NBF in an appropriate hazardous waste container at your facility. Store the biopsy in the vial with 70% histology alcohol at 4°C until shipping. Please ship immediately to the analytical laboratory below for further processing into FFPE tumor blocks. Do not ship specimens in formalin. Tumor tissue needs to be embedded within 1 week of biopsy.

9.2.1.3 Shipping of Specimen(s)

Supplies for preparing and shipping of tissue samples should be provided by the sites. The central lab will provide labels for specimens, a requisition form to submit along with the tissue sample for mesothelin testing, and airway bills for shipping. Samples should be shipped as soon as they are available.

9.2.1.4 Site Performing Correlative Study

Mesothelin testing will be performed by Hematogenix. Results will be available on the central lab's HematoPass portal. Results should be available within 3-5 days of sample receipt.

9.3 Integrated Correlative Studies

9.3.1 Anetumab Ravidansine Pharmacokinetics (PKs)

Anetumab Ravidansine PK studies consist of three analyses:

1. BAY 94-9343 ADC
2. BAY 94-9343 TAB (Total Antibody)
3. DM4 (BAY 1006640) and DM4-Me (BYA1006441)

Refer to Covance lab manual for additional instructions.

9.3.1.1 Collection of Specimen(s)

a. BAY 94-9343 ADC and BAY 94-9343 TAB

Collect minimum 2.7 mL whole blood in 3 mL lavender top EDTA tubes at the collection time points listed in Section 9.1.

b. DM4 (BAY 1006640) and DM4-Me (BYA1006441)

Collect minimum 2.7 mL whole blood in 2.7 mL lavender top EDTA monovette at the collection time points listed in Section 9.1.

9.3.1.2 Handling of Specimens

a. BAY 94-9343 ADC and BAY 94-9343 TAB

Store collected blood in refrigerator until centrifugation. Centrifuge at 2000g at ~4°C for 10 min. Transfer plasma equally into labeled polypropylene tubes; each tube must contain at least 0.2 mL of plasma. *Total duration time between sample collection at room temperature and final storage MUST NOT exceed 60 min.* Store frozen at < -15°C until shipping.

b. DM4 (BAY 1006640) and DM4-Me (BYA1006441)

Immediately centrifuge at 2000g at ~4°C for 10 min. Transfer exactly 0.8 mL of plasma into labeled plasma collection tube prefilled with 0.08 mL 10% aqueous formic acid); thoroughly vortex. *Total duration time between sample collection at room temperature and final storage MUST NOT exceed 30 min.* Store frozen at < -15°C until shipping.

9.3.1.3 Shipping of Specimen(s)

All samples to be stored in freezer as outlined in handling instruction and then batched and shipped to Covance using air bills and requisitions provided every 3 months on dry ice according to instructions.

